2.3 Sample Size and Power

Each active treatment group will be compared with the placebo group at the two-sided 0.05 significance level; 85 subjects per arm provides approximately 80% power to detect a difference in the proportions of subjects achieving the primary efficacy endpoint of 39.5% in any MSDC-0602K group versus 20% response rate in the placebo group. These response rates are similar to effects reported after 18 months daily treatment with 45 mg pioglitazone (58% response) or placebo (17% response) in subjects with pre-diabetes or T2DM (Cusi 2014); after 96 weeks daily treatment with 30 mg pioglitazone (34% response) or placebo (19%) in non-diabetic adults with NASH in the PIVENS study (Sanyal 2010); and in the GOLDEN study, after 52 weeks daily

treatment with 120 mg elafibranor (32% response) or placebo (21%) in the subset of NASH subjects with a baseline NAS ≥ 4 (Ratziu 2016). Assuming 10% of subjects will not complete the 12-month assessment due to early dropout, 380 subjects will be randomized to the study. Sample size calculations were made using nQuery Advisor® (Statistical Solutions Ltd., Boston, MA, USA).

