7 STATISTICAL METHODS

7.1 General Principles

All data processing, summarization and analyses will be performed using Version 9.3 (or later) of the SAS® (SAS Institute, Cary, NC) statistical software package.

Unless specified otherwise, data will be displayed using the following treatment group labels, in the order presented:

- Placebo
- MSDC-0602K 62.5 mg
- MSDC-0602K 125 mg
- MSDC-0602K 250 mg
- Total (if applicable)

All data collected will be presented in listings by treatment group, site, subject, and visit (where applicable), unless otherwise specified.

Data will be presented in summary tables by treatment group, assessment and visit (where applicable).

Descriptive summary statistics for continuous variables will include the number of observations (N), mean, standard deviation (SD), median, 25th and 75th percentiles, minimum and maximum.

Descriptive summary statistics for categorical variables will include frequency counts and percentages [n (%)]. Unless stated otherwise in the table shells, the denominator for percentage calculations will be the number of subjects in the analysis population with a non-missing value.

Dates will be displayed as DDMMYYYY.

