7.9 Safety

7.9.1 Adverse Events

All adverse events (AEs) recorded on the eCRF will be coded using the MedDRA dictionary Version 19.0 (or a later version if updated during the study) and classified as treatment-emergent AEs (TEAEs) as follows:

- TEAEs are events with start date on or after the date of first dose of study treatment and up to 14 days after date of last dose of study treatment or events with start date prior to the date of first dose of study treatment whose severity worsens on or after the date of first dose of study treatment.

Listings of Serious AEs (SAEs), AEs leading to discontinuation of study treatment, and AEs resulting in death will be produced by treatment group. Adjudicated cause of death will be described. AEs with an onset between signing of informed consent and study drug initiation, and those with onset more than 14 days after the last dose of study drug will be listed separately.

The number and percentage of subjects reporting each TEAE will be summarized by System Organ Class (SOC) and Preferred Term (PT) by treatment group and overall in the SAF population. Each subject will be counted only once within each PT or SOC and recording period. If a subject experiences more than one AE within a PT for the same recording period, only the AE with the strongest relationship or the worst severity, as appropriate, will be included in the summaries of relationship and severity. AEs with missing classifications regarding relationship to study drug and start date greater or equal to start of study drug will be considered as related to study drug. AEs that were reported to be at least possibly related to study drug will be considered as related to study drug.

Tables will be produced for the following TEAEs overall and by SOC and PT, preceded by an overview table:

- Any TEAE
- Most common TEAEs ($\geq 5\%$ in any treatment group)
- TEAEs by maximum severity
- TEAE related to study drug
- TEAEs related to study drug by maximum severity
- TEAE leading to study drug discontinuation
- TEAEs related to study drug and leading to study drug discontinuation
- TEAEs leading to study drug interruption
- Any TESAE (treatment-emergent serious AE)
- TESAE related to study drug
- TESAE leading to study drug discontinuation
- TESAEs related to study drug and leading to study drug discontinuation
- TESAEs leading to study drug interruption

- TESAE leading to death

No statistical comparisons of TEAEs between treatment groups will be performed.

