7.9.6 Major Adverse Cardiovascular Events and Liver Events

A Clinical Events Committee (CEC) will adjudicate Major Adverse Cardiovascular Events (MACE), which are defined as death, adjudicated non-fatal MI or USA hospitalization, adjudicated hospital admission for HF, or adjudicated non-fatal ischemic stroke. Time from baseline to occurrence of first event will be computed in days. Subjects without an event will be censored at the earlier of the end of the time period of interest and the last contact date.

Time to first MACE through 14 days after last dose of study treatment will be presented as number of events with Kaplan-Meier estimates of the cumulative risk of event. Hazard ratios and corresponding 95% confidence intervals comparing each active treatment group to placebo will be estimated from a Cox proportional hazards model including a factor for treatment group; and the model will be stratified by randomization stratification factors (presence of diabetes mellitus, Vitamin E \geq 400 IU, and baseline fibrosis F1 versus F2/F3) if the number of events permits. Treatment groups will be compared using a log-rank test.

Similarly, time to first MACE or adjudicated liver event (ascites, hepatic encephalopathy, variceal hemorrhage, hepatocellular carcinoma, or liver transplant) through 14 days after last dose of study treatment will be analyzed and presented.

Results will also be provided for each component of these composite events. For non-fatal events, subjects who die before the time point of interest and who did not reach the event of interest before death will be censored on the day of death. Results will be presented through 14 days after last dose of study treatment for:

- Time to death
- Time to first adjudicated non-fatal MI
- Time to first adjudicated USA hospitalization
- Time to first adjudicated hospital admission for HF
- Time to first adjudicated non-fatal ischemic stroke
- Time to first adjudicated liver event

In addition, deaths will be presented in a listing including investigator-reported data and the adjudicated primary cause of death.

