7.9.7 Severe Hypoglycemic Events

The CEC will also adjudicate severe hypoglycemia events. The total number of events and the number and percentage of subjects with any event through 14 days after last dose of study treatment will be presented by treatment group, as adjudicated by the CEC.

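### SAP 7.9.6: dose-by-dose Cox hazard ratios are the only effect estimates for MACE and MACE-or-liver events, with no pooled MSDC-0602K contrast and no method for arms with few or no events

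*SAP*

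**What the plan says.** SAP 7.9.6 defines MACE as death, non-fatal MI or unstable-angina hospitalization, heart-failure admission or non-fatal ischemic stroke. First events are counted up to 14 days after the last dose. The section plans event numbers with Kaplan-Meier cumulative risk, and then: "Hazard ratios and corresponding 95% confidence intervals comparing each active treatment group to placebo will be estimated from a Cox proportional hazards model". The model is to be stratified by the randomization factors if there are enough events. That condition governs the stratification only, not whether the model is fitted. A log-rank test of the treatment groups follows, without saying whether it is one test across four arms or three pairwise tests.

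MACE-or-liver event is handled in the same way. Results are also promised for six components, but the text does not say outright that a hazard ratio will be fitted to each.

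The default display columns in SAP 7.1 are placebo, the three doses and, where applicable, a total. SAP 7.9.1 has TEAEs "summarized by System Organ Class (SOC) and Preferred Term (PT) by treatment group and overall in the SAF population". In SAP 7.9.7, severe hypoglycemia counts "will be presented by treatment group, as adjudicated by the CEC". SAP 7.9.8 likewise shows fractures by treatment group. None of these sections defines a combined MSDC-0602K group, and a total or overall column includes placebo.

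**The concern.** Safety is half of the study objective (SAP 2.1), and the documents themselves point to some of the harms. Protocol 2.1 contrasts the drug with earlier insulin sensitizers on volume expansion, and Protocol 6.3 lists symptoms of CHF among the reasons for stopping study drug.

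With about 95 subjects per arm for about a year, some of these outcomes may have very few events. An ordinary Cox hazard ratio with a Wald interval fails when either compared arm has no event. The SAP guards against sparsity elsewhere: SAP 8 reduces the CMH stratification to avoid thin cells, for an endpoint assumed to occur in 20% to 39.5% of subjects. The adjudicated events have no such safeguard beyond the stratification condition.

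SAP 8 also says that adjudication was introduced after the protocol was finalized, so the SAP is where these analyses must be specified. At stake is whether the report will give a usable interval for drug against placebo on rare harms, and whether the active subjects are ever set against placebo together.

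**Working it through.** **The plan's own figure.** SAP 2.3 says "85 subjects per arm provides approximately 80% power to detect a difference in the proportions of subjects achieving" the primary endpoint, at "39.5% in any MSDC-0602K group versus 20% response rate in the placebo group". The pooled response rate is (0.20 + 0.395)/2 = 0.2975. The null standard error is √(2 × 0.2975 × 0.7025/85) = 0.0701. The alternative standard error is √((0.20 × 0.80 + 0.395 × 0.605)/85) = 0.0685. So z = (0.195 − 1.96 × 0.0701)/0.0685 = 0.84, which gives 80.0% power. For dropout, 340/0.90 = 378 against 380 stated. Both reproduce. They fix the sample size but say nothing about safety events: the documents give no event rate, event count or power for these.

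**Inputs for the event check.**
- Arm size: 380 randomized 1:1:1:1 (SAP 2.2 and 2.3), so 380/4 = 95 per arm and 3 × 95 = 285 on active drug. All randomized subjects are taken as treated.
- Cumulative risk r over the event window: assumed, shown as a range, and equal in all arms.

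**Formulas.**
- Empty arm: P0 = (1 − r)^95.
- A given dose-placebo ratio has at least one empty arm: 1 − (1 − P0)².
- All three dose ratios estimable: (1 − P0)⁴.
- The pooled-placebo ratio has an empty side: 1 − (1 − P0)(1 − P0³), because (1 − r)^285 = P0³.

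| Assumed r | P0 | Dose ratio has an empty arm | All three estimable | Pooled ratio has an empty side |
|---|---|---|---|---|
| 0.5% | 0.621 | 86% | 2% | 71% |
| 1% | 0.385 | 62% | 14% | 42% |
| 2% | 0.147 | 27% | 53% | 15% |
| 3% | 0.055 | 11% | 80% | 6% |

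Worked at 1%: 0.99^95 = 0.385; 1 − 0.615² = 0.62; 1 − 0.615 × (1 − 0.057) = 0.42.

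**Break-even.** The dose ratio is non-estimable with probability one half when (1 − P0)² = 0.5, so P0 = 0.293 and r = 1 − 0.293^(1/95) = 1.28%. For the pooled ratio the break-even is 0.84%. If the true hazard ratio is 2, the dose-level break-even falls to a placebo risk of about 0.95%.

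**How many ratios.** The two composites give 2 × 3 = 6 ratios. If the Cox model is also fitted to the six components, there are 8 × 3 = 24. For illustration, let each of the five non-liver components carry one fifth of the MACE risk and liver events one tenth of it. Summing 3(1 − P0)² over the eight outcomes, the expected number estimable is 2.9 of 24 at a MACE risk of 1%, 6.1 at 2% and 12.0 at 5%.

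**Precision when every arm has d events.** Var(log HR) is approximately 1/d + 1/d for one dose and 1/d + 1/(3d) pooled, a ratio of (4/3)/2 = 0.667. With d = 3, the 95% interval factor falls from exp(1.96 × √(2/3)) = 4.95 to exp(1.96 × √(4/9)) = 3.69.

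**The case against.** The strongest reply is that the plan is not blind to rare events. Counts and Kaplan-Meier estimates appear for every arm, and a log-rank test stays defined when one arm is empty; if global, it uses all four arms. A reader might therefore wrongly infer that Cox ratios are the only comparison. They are the only effect estimates. A log-rank test gives no effect size, and a global one is not a drug-versus-placebo contrast.

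Second, a per-dose display matches an objective framed around three doses, SAP 7.9.1 rules out statistical comparison of TEAEs, and the SAP 7.1 columns are defaults, with table shells that are not in the documents. This stands in part. Severe hypoglycemia and fractures get counts, not a Cox model, so for them the gap is only the missing column. A shell might contain an all-active column, but the SAP text does not specify one.

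Third, it is tempting to say that separate arms hide cases: a 1% harm shows at least one case with probability 1 − 0.99^95 = 62% in one arm and 1 − 0.99^285 = 94% in three. That measures no loss from this plan. All 285 active subjects are observed and reported, and a reader can add three columns.

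Fourth, pooling helps only partly, as the table shows. This stands, and it is why a sparse-event method is needed as well.

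**Conclusion.** Two gaps stand on the SAP text: no all-MSDC-0602K versus placebo contrast, and no alternative estimate when an arm has few or no events. At equal risk and 95 per arm, a dose-placebo ratio is more likely than not non-estimable only below about 1.3% cumulative risk. Pooling cuts the variance of the log hazard ratio by one third at equal event counts, but it cannot rescue the ratio when placebo has no event.

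Two stronger readings should be resisted.
- A reader might infer that most of the planned ratios will fail. That needs an event rate the documents do not give. It is plausible for single components and liver events, since a history of cirrhosis or decompensation is excluded (Protocol 5.2). It is not established for the MACE composite, which includes any death, unstable-angina and heart-failure admissions. Coronary events are excluded only within six months before randomization, and HbA1c up to 9.5% and BMI up to 50 kg/m² are allowed (Protocol 5.1).
- A reader might infer that an empty placebo arm makes all three ratios infinite. Where the dose arm is also empty, the ratio is undefined.

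This is a cheap and worthwhile improvement to the safety reporting. It does not affect the primary efficacy analysis.

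**What to change.** Keep every per-dose result and make four changes to the SAP.

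1. Add an *All MSDC-0602K* column to the TEAE, TESAE, MACE and liver, severe hypoglycemia and fracture tables, beside or in place of the overall column.
2. In 7.9.6, add a pooled-active versus placebo contrast. State also whether the Cox model is fitted to each of the six components.
3. Set a sparse-event rule. When a compared arm has few events (for example, fewer than 5), replace the Wald Cox interval with an exact risk difference and its confidence interval, or with a Firth-penalised Cox estimate and profile-likelihood interval. Where both compared arms are empty, only the risk difference yields an interval.
4. State whether the log-rank test is global or pairwise.

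The cost is SAP wording and one column per table; no new data are needed. The downside is that pooling can dilute a harm confined to one dose, which is why the per-dose rows stay.

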7.9.7 Severe Hypoglycemic Events

The CEC will also adjudicate severe hypoglycemia events. The total number of events and the number and percentage of subjects with any event through 14 days after last dose of study treatment will be presented by treatment group, as adjudicated by the CEC.

7.9.8 Bone Fractures Requiring Surgery or Hospitalization

The number of fractures requiring surgery or hospitalization as well as the number and percentage of subjects with any fracture requiring surgery or hospitalization, as reported by the investigator, through 14 days after last dose of study treatment will be presented by treatment group.

7.10 Interim Analysis

An interim analysis of exploratory and safety endpoints is planned after all subjects have been randomized into the study and 6-month data are available for a minimum of 300 randomized subjects. Changes in selected serum biomarkers from baseline to 6 months will be assessed. Descriptive summary statistics by treatment group will be presented and results shared with a limited group of people to be identified by the Sponsor. The treatment assignments of individual subjects will not be presented, i.e., data listings will not be included for this interim analysis. Details will be provided in a separate SAP for the interim analysis.

8 CHANGES FROM PROTOCOL-SPECIFIED ANALYSES

The specialty biomarkers to be analyzed were changed following finalization of the protocol. The following biomarker described in the protocol will not be analyzed: CK-18 [M30]. Changes from baseline in biomarkers and indirect measures of apoptosis and liver fibrosis at 6 months were added as pre-specified exploratory efficacy endpoints.

The exploratory endpoint “Changes from baseline relative to placebo at 12 months in the pathologist’s general impression” has been corrected to reporting the general impression as provided by the central histopathologist: NASH diagnosis 1) confirmed, or 2) cannot be confirmed. While the local pathologists provide the information as initially planned in the protocol, this is not available from the central histopathologist.

The last exploratory endpoint “Changes from baseline relative to placebo in subjects with PNPLA3 variants and other genotypes” has been removed from the list as it is not an endpoint per se but refers to subgroup analyses of efficacy endpoints with respect to genetic variants (see Section 7.8.3).

The definition of the per protocol analysis set was expanded to allow possible exclusion of subjects based on trough levels of study drug and its metabolite.

For the derivation of treatment compliance, the last dose date will be used instead of last dose date +14 days to define the end of the treatment period if study treatment was discontinued early. The derivation of compliance measures per treatment period as well as production of listings and/or presentation of summary statistics of per-period and of overall compliance will be omitted. The rationale for these changes is that because capsule counts are known to be unreliable and despite our best efforts to clean the data there are still discrepancies that cannot be resolved.

The methods for efficacy analysis have been clarified. Due to the expected highly unequal marginal distribution of the stratification factor “use of Vitamin E \geq 400 IU” (Yes vs. No) this factor was removed from all logistic regression models (except for the corresponding subgroup analysis).

The pairwise comparisons of active treatment versus placebo through CMH tests have been revised to only include stratification for presence of diabetes mellitus as to avoid overly sparse cross-classification frequencies of the originally included stratification factors, treatment, and outcome.

According to the protocol, sensitivity analyses had been planned for the primary and secondary dichotomous efficacy endpoints examining the addition of sex to the primary logistic regression

models. The sensitivity analyses have been updated to include age at baseline as well because age is expected to be associated with response, and to exclude use of Vitamin E ≥ 400 IU similar to the primary analysis. Further sensitivity analyses have been added to examine different time restrictions for the biopsies taken at 12 months.

Adjudication of Major Adverse Cardiovascular Events, liver events, and severe hypoglycemic events by a Clinical Events Committee, and collection of information regarding fractures were introduced after finalization of the protocol. Corresponding analyses have been added to the SAP.

10 APPENDIX

Schedule of Activities

Visit Number	Screen ¹	Treatment							Follow-up
		1	2	3	4	5	6	7	8
Study Months	Randomization	1	2	3	6	9	12		
Study Day Window	-42 to -1	1	30	60	90	180	270	360	374
		N/A	± 7 days						± 3 days
General Activities									
Informed Consent	X								
Medical History	X								
Complete Physical Examination ²	X								X
Limited Physical Examination ²		X	X	X	X	X	X	X	
Vital signs ³	X	X	X	X	X	X	X	X	X
12-lead ECG	X					X		X	X
Pregnancy test (females only)	X	X							X
FSH (post-menopausal females only)	X								
FibroScan ⁴	X							X	
Liver Biopsy ⁵	X							X	
Randomization		X							
Dietary guidance and assessment of alcohol intake ⁶	X	X	X	X	X	X	X	X	
Adverse event review	X	X	X	X	X	X	X	X	X
Concomitant medication review	X	X	X	X	X	X	X	X	
Monthly phone assessment ⁷					X	X	X		
Study drug dispensing ⁸		X			X	X	X		
Central Lab Evaluations									
Hematology & serum chemistry ^{9, 10}	X	X	X	X	X	X	X	X	X
Liver function tests	X	X	X	X	X	X	X	X	
Urinalysis	X	X			X	X	X	X	X
HMW adiponectin, hsCRP, CK-18 [M65], osteocalcin, and CTX		X				X		X	
Fibrosure, ELF score, APRI, FIB-4 index, Pro-C3		X				X		X	
Serum sample for NMR analysis		X						X	
Blood sample for genotyping analyses (optional) ¹¹		X							
Plasma samples for future miRNA and biomarker testing ¹²		X				X		X	
Trough PK sample ¹³			X		X	X	X	X	

1. ICF may be obtained before the 42-day screening window. Re-testing is allowed within the 42-day Screening period if, in the opinion of the Investigator, the subject may become eligible upon repeat testing.

2. Height and body weight are collected at Screening only; body weight, waist circumference measured midway between the lowest rib and the iliac crest, and signs of peripheral edema are collected at all study visits.

3. Vital sign measurements including seated BP and heart rate are collected at every visit; oral temperature is collected at screening, pre-dose on Day 1 and Visit 8.

4. FibroScan is required within 90 days prior to or during Screening.

Statistical Analysis Plan

Version: Final 1.5

Date of Issue: 16-May-2019

Cirius Protocol No. MSDC-0602K-C009NASH

5. A qualifying liver biopsy is required within 9 months prior to Screening. If a historical liver biopsy result is not available within this period, a liver biopsy must be performed during Screening for eligible subjects who meet all other entry criteria. A liver biopsy is also performed at Visit 7.
6. Non-diabetic subjects are provided the NCEP dietary guidance at Screening and diabetic subjects are provided the ADA dietary guidance at Screening. Guidance regarding alcohol consumption is also provided to all subjects at Screening. All subjects are assessed for compliance with dietary guidelines and alcohol consumption at each visit.
7. Study staff will contact the subjects by phone every month between Visits 4-7 to inquire about adverse events and serious adverse events.
8. 3 bottles dispensed at Visits 1, 4, 5, and 6.
9. Minimum 10-hour fasting blood sample collected pre-dose.
10. FPG and HbA1c will also be measured at Visits 1, 5 and 7.
11. A separate genotyping informed consent is required to enable collection of blood sample for genotyping analyses.
12. At each timepoint, plasma samples will be split into two separate vials and stored for biomarker testing, including miRNA, to be determined at a later date.
13. Pre-dose trough PK sample collected for analysis of MSDC-0602 and MSDC-0597.
